5.3 Lifestyle Considerations

5.3.1 Meals and Dietary Restrictions

5.3.1.1 Diet Restrictions

Fasting requirements for study procedures, such as but not limited to laboratory safety evaluations are specified in Section 8.0.

Each study drug administration will need to be taken with 240 mL of water after an 8 hour fast. Water will be restricted 1 hour prior to and 1 hour after study drug administration. Subjects will remain fasting until 1 hour post dose.

On full PK sampling days and/or 24-hour Holter monitoring days, participants will fast from all food and drinks, except water, for at least 8 hours prior to study drug administration until 1 hour post-dose. Participants will fast from all food and drinks except water between study drug administration and the first scheduled meal. Meals and snack(s) will be provided by the investigator at time points indicated in the SoA. Participants will fast from all food and drinks except water between meals and snacks. The caloric content and composition of meals will be the same on each full PK sampling and/or Holter evaluation day in each panel. Meals and snacks will be served after any coinciding Holter and/or PK procedure. After the Day 15 (Panel D) or Day 18 (Panel A, Panel B and Panel C) 48-hour post-dose procedures have been completed (Day 17 or Day 20, respectively for Panel D or Panel A, Panel B, Panel C), subsequent meals and snacks will be unrestricted in caloric content, composition and timing.

Meal and water restrictions on Day -1 (Panels A, B and D only) will be time-matched to those timepoints on 24-hour Holter/PK days when treatment is administered. Similarly, meal and water restrictions will be time-matched on Day 19 and Day 20 (Panel A and B) and Day 16 and Day 17 (Panel D) to 24-hour Holter/PK days when treatment is administered.

On intermediate days, participants will fast from all food and drinks, except water, for at least 8 hours prior to study drug administration. Participants will remain fasted until 1 hour post-dose. Meals and snacks should be standardized for caloric content, composition and timing. Meals and snacks should be served after any scheduled ECG procedure.

5.3.1.2 Fruit Juice Restrictions

Participants will refrain from the consumption of grapefruit juice, grapefruits, and grapefruit products beginning approximately 2 weeks prior to administration of the initial dose of study drug, throughout the study until 48 hours following last dose administration.

On full PK sampling and/or Holter days, participants will refrain from the consumption of all fruit juices 24 hours prior to study drug administration.

On intermediate days, the consumption of all fruits and fruit juices (except for grapefruit, grapefruit juices, and grapefruit products) is allowed.

5.3.2 Caffeine, Alcohol, and Tobacco Restrictions

5.3.2.1 Caffeine Restrictions

Participants will refrain from consumption of caffeinated beverages or xanthine-containing products from 12 hours prior to the prestudy and poststudy visits.

On full PK sampling and/or Holter days (Panels A and B: Day -1, Day 7, Day 10, Day 13, Day 16, Day 18 and Day 19; Panel C: Day 9, Day 12, Day 15 and Day 18; Panel D: Day -1, Day 1, Day 4, Day 7, Day 10, Day 13, Day 15 and Day 16), participants will be permitted to consume approximately 2 units of caffeinated beverages or xanthine-containing products only between 1 hour and 2 hours post dose. Otherwise, participants will refrain from consumption of such products 8 hours prior to study drug administration until the 24- hour postdose ECG/PK assessment is complete.

On intermediate days, caffeinated beverages or xanthine-containing products will be limited to no more than 6 units per day amounts (>6 units: 1 unit = 120 mg of caffeine).

5.3.2.2 Alcohol Restrictions

Participants will refrain from consumption of alcohol 24 hours prior to the prestudy and poststudy visits. During the in-house period, consumption of alcohol is not allowed. At all other times, alcohol consumption is limited to no more than approximately 3 alcoholic beverages or equivalent (1 glass is approximately equivalent to: beer [354 mL/12 ounces], wine [118 mL/4 ounces], or distilled spirits [29.5 mL/1 ounce]) per day.

5.3.2.3 Tobacco Restrictions

For Panel A (healthy participants), smoking (and/or the use of nicotine/nicotine-containing products) is not permitted during the study.

For Panel B, Panel C and Panel D (participants with schizophrenia), smoking restrictions (and if applicable, the use of nicotine/nicotine-containing products) defined by the CRU will be followed during the study.

5.3.3 Activity Restrictions

Participants will avoid unaccustomed strenuous physical activity (i.e., weight lifting, running, bicycling, etc.) from the prestudy (screening) visit until administration of the initial dose of study drug, throughout the study (including washout intervals between treatment periods) and until the poststudy visit.

5.4 Screen Failures

Screen failures are defined as participants who consent to participate in the clinical study but are not subsequently randomized in the study. A minimal set of screen failure information may be included, as outlined in the electronic case report forms (eCRF) entry guidelines. Minimal information may include demography, screen failure details, eligibility criteria, and any AEs or SAEs meeting reporting requirements.

5.5 Participant Replacement Strategy

A participant who discontinues from study intervention or withdraws from the study in Panel A or Panel B will not be replaced.

If a participant discontinues from study intervention or withdraws from the study in Panel C or Panel D, a replacement participant may be enrolled if deemed appropriate by the investigator and Sponsor. The replacement participant will generally receive the same intervention or intervention sequence (as appropriate) as the participant being replaced. The replacement participant will be assigned a unique treatment/randomization number. The study site should contact the Sponsor for the replacement participant's treatment/randomization number.

The replacement participant may begin dosing at the subsequent dose level for that panel, based on investigator and Sponsor review and discussion.

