4 STUDY DESIGN

4.1 Overall Design

Specific procedures to be performed during the study, as well as their prescribed times and associated visit windows, are outlined in the SoA in Section 1.3. Details of each procedure are provided in Section 8.

This is a four-panel, randomized, placebo-controlled, parallel-group, multiple-dose, double-blinded, safety, tolerability, PK and QTc study of MK-8189 in participants with schizophrenia and healthy participants.

Panel A will enroll up to 16 healthy participants (8 Japanese and 8 non-Japanese) and Panel B will enroll up to 16 participants with schizophrenia or schizoaffective disorder to ensure at least 12 completers per group. Panel C will enroll up to 12 participants with schizophrenia/schizoaffective disorder and Panel D will enroll up to 20 participants with schizophrenia; participants may be replaced at the discretion of the Sponsor in consultation with the principal investigator. Participants will be randomized to MK-8189 or matched-placebo in a ratio of 3:1 (Panels A, B and C) and 3:2 (Panel D) according to a computer generated allocation schedule; within Panel A, 6 Japanese and 6 non-Japanese will be randomized to MK-8189 and 2 Japanese and 2 non-Japanese will be randomized to receive placebo according to the computer generated allocation schedule.

Participants with schizophrenia in Panel B and Panel D will be washed off their antipsychotic medication. The washout may start with a down titration of the antipsychotic treatment during the screening phase per direction of the investigator. Participants in Panel B and Panel D should not receive antipsychotics for at least 5 days or 3 half-lives (whichever is longer) prior to Day -1 Holter assessments. If deemed appropriate by the investigator, a participant may begin their washout as an outpatient, but should be confined within a week of starting the washout and minimally beginning on Day -6. In Panel C, participants with schizophrenia will remain on their study permitted atypical antipsychotic (AAP).

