Panels A, B and C: Beginning on Day 1, participants randomized to MK-8189 will begin to receive MK-8189 QD and will be titrated from 4 mg to 24 mg over the course of an 18 day treatment period as follows: 1 x 4 mg tablet Days 1-3, 2 x 4 mg tablets Days 4-6, 3 x 4 mg tablets Days 7-9, 4 x 4 mg tablets Days 10-12, 5 x 4 mg tablets Days 13-15 and 6 x 4 mg tablets Days 16-18. Participants randomized to placebo will receive the same number of tablets matching the 4 mg tablet of MK-8189 as the active group. Dose titration decisions for each participant will occur, after 3 days of dosing per dose level, jointly between the investigator and Sponsor.

Panel D: Beginning on Day 1, participants randomized to MK-8189 will begin to receive MK-8189 QD and will be titrated from 8 mg to 48 mg over the course of a 15 day treatment period as follows: 2 x 4 mg tablets Days 1-3, 4 x 4 mg tablets Days 4-6, 6 x 4 mg tablets Days 7-9, 9 x 4 mg tablets Days 10-12 and 12 x 4 mg tablets Days 13-15. Participants randomized to placebo will receive the same number of tablets matching the 4 mg tablet of

MK-8189 as the active group. Dose titration decisions for each participant will occur, after 3 days of dosing per dose level, jointly between the investigator and Sponsor.

In Panel D, a small cohort (n=4) will initially be dosed with 8 mg to confirm tolerability prior to dosing the remainder of the cohort. Tolerability will be assessed following the second dose of 8 mg before the remainder of the panel is dosed; depending on tolerability, the remainder of the panel may i) be dosed starting with 8 mg, ii) a small cohort of the remainder of the panel may be dosed starting with 8 mg, or iii) the starting dose may be adjusted downward to 4 mg. The decision on how to proceed will be made by the principal investigator jointly with the Sponsor and documented in a protocol clarification letter. If any of the panel begins dosing at 4 mg, the following titration schedule may be followed: 1 x 4 mg tablets Days 1-3, 2 x 4 mg tablets Days 4-6, 4 x 4 mg tablets Days 7-9, 6 x 4 mg tablets Days 10-12 and 12 x 4 mg tablets Day 13-15.

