If a participant does not tolerate escalation to the next dose, the participant may be titrated down to the previous dose (Panel A, B, C or D) or intermediate dose (Panel D). In addition, as discussed above, if the initial dosing cohort of Panel D or subsequent dosing cohort(s) does not tolerate the starting dose of 8 mg, subjects may be down-titrated to 4 mg. If appropriate medical care necessitates a down-dose, the investigator may do so independent of consultation with the Sponsor. If the participant tolerates continued dosing following down-titration, the participant may continue in the trial at that dose until study completion or may be re-challenged at a higher dose. Re-challenges are only to occur on regularly scheduled dose titration days, i.e. Day 4, Day 7, Day 10, etc. and will not extend the participant's time in the study. Participants will be followed for approximately 2 weeks after the last study treatment dose.

Panel A, healthy participants, will be confined to the clinical research unit (CRU) beginning on Day -2 through Day 21.

Participants with schizophrenia in Panel B and Panel D have a risk to experience exacerbations in psychotic symptoms both during the washout period as well as during the MK-8189 treatment period. To mitigate this risk, only participants with schizophrenia in the non-acute phase of their illness, with the onset of the first episode being no less than 2 years prior to study entry, will be recruited for study.

Panel B and Panel D, participants with schizophrenia, will be confined to the CRU within a week of beginning their antipsychotic medication washout and for at least the last 5 days of their washout (i.e. confinement will begin on Day -6 or earlier) and during the MK-8189 treatment to provide an enhanced level of participant supervision. If needed, rescue medication will be provided to treat withdrawal symptoms (see Section 6.5.1). Participants showing exacerbations in psychotic symptoms during the washout period will be re-evaluated for participation and referred for additional treatment as indicated.

Panel C, participants with schizophrenia, will be confined to the CRU beginning on Day -1 through Day 21.

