Doses will be titrated up to 24 mg (Panels A, B and C) and 48 mg (Panel D) of MK-8189 to improve tolerability and minimize EPS (see Section 4.3) and a matched placebo-control will be included to reduce bias with regards to the patient reporting and investigator assessment of AEs. In addition, inclusion of a placebo cohort will also control for potential bias introduced by study procedures and to increase the power to exclude modest QTc effects in a study with a relatively small sample size.

In Panel A, Panel B and Panel D, Holter monitoring for 24 hour periods and ECG interval extraction at pre-specified timepoints for review by a blinded central reader will be included to support the rigorous evaluation of QT effect in accordance with the QT white paper [Garnett, C., et al 2017]. Replicate ECGs (triplicate) extracted from 24-hour Holter tracings and a centralized core laboratory to assess QTc interval will reduce variability. Pharmacokinetics will also be evaluated on Holter days to support a concentration-QTc analysis allowing for characterization of the exposure-QTc relationship at a multiple above expected therapeutic concentrations. In Panel C, 12-lead triplicate ECGs and PK will be evaluated at timepoints expected to coincide with peak concentrations at doses ≥ 12 mg to monitor safety and to explore the QTc-concentration relationship in the setting of add-on therapy (Panel C).

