4.3.1 Starting Dose for This Study

A 4 mg starting dose with the CR tablet formulation has been shown to be well tolerated in previous clinical trials in schizophrenia including the MAD study (P003) as well as the POC study (P005). Since the safety and tolerability profile in healthy participants and participants with schizophrenia is similar, a 4 mg dose has been selected for the current protocol in Panels A, B and C. As higher doses are being proposed for Phase 2, it is important to explore optimized titration schedules, therefore Panel D will explore a starting dose of 8 mg. Initiating the dose at 8 mg is supported by the tolerability observed in Panel A, Panel B and Panel C. In addition, the average receptor occupancy increase from 4 to 8 mg is approximately [REDACTED] with a large degree of overlap between doses (see figure below in section 4.3.3), thus the tolerability is expected to be similar between the two starting doses. As described in the study design (Section 4.1), a small cohort (n=4) will initially be dosed with 8 mg to confirm tolerability prior to dosing the remainder of the cohort.

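### Replacements in Panels C and D may skip titration: the permitted first dose is undefined and runs from 2-fold to 6-fold the planned start

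*Combined protocol and SAP*

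**What the plan says.** Section 5.5 allows replacements in Panels C and D only. On assignment it states: "The replacement participant will generally receive the same intervention or intervention sequence (as appropriate) as the participant being replaced". It then adds: "The replacement participant may begin dosing at the subsequent dose level for that panel, based on investigator and Sponsor review and discussion". Nothing further is said about the first dose, the titration that follows, or which Schedule of Activities days apply to someone who starts late.

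On starting doses, Section 4.3.1 says that "a 4 mg dose has been selected for the current protocol in Panels A, B and C". For Panel D it proposes 8 mg and compares this with a 4 mg start: "thus the tolerability is expected to be similar between the two starting doses". Even so, Section 4.1 provides that in Panel D "a small cohort (n=4) will initially be dosed with 8 mg to confirm tolerability prior to dosing the remainder of the cohort", with a fallback to 4 mg and the decision recorded in a protocol clarification letter.

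Section 4.2 gives tolerability and EPS as the reasons for titrating. Section 4.3.3 relies on a step every 3 days to prevent EPS or let it settle before the next step. Section 6.6 makes each titration decision for the individual participant, after 3 days at a level, on safety data from earlier levels.

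**The concern.** The last sentence of Section 5.5 exists only to let a replacement omit the lower dose levels. It therefore sets aside, for that participant, the protocol's main protection against EPS. It does so without defining the permitted level and without giving the investigator and Sponsor a criterion to decide by.

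At stake is the safety of an untitrated participant on active drug. That person could receive, as a first-ever dose, a level that others reach only after days or weeks at lower doses. There is also a scientific cost in Panel D: Section 4.3.3 presents that panel as a test of a faster titration scheme, and a late starter does not test it.

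**Working it through.** **Inputs** (Section 4.1 and Tables 3 and 4 in Section 6.3.1). Each level lasts 3 days.

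- Panel C: 4, 8, 12, 16, 20, 24 mg (18 days).
- Panel D, main schedule: 8, 16, 24, 36, 48 mg (15 days).
- Panel D, fallback schedule: 4, 8, 16, 24, 48 mg (15 days).

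**Check against the protocol's own figures.** Section 4.3.3 describes the fallback's last two steps as 1.5-fold and 2-fold. 24/16 = 1.5 and 48/24 = 2, so the ladder is read correctly.

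**Largest planned step between consecutive levels.** Panel C: 8/4 = 2. Panel D: 16/8 = 2. Fallback: 8/4 = 16/8 = 48/24 = 2. No planned step exceeds 2-fold, and each follows 3 days at the lower level.

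**Reading 1: the level after the panel's first.** Fold = second level / first level. Panel C: 8/4 = 2. Panel D: 16/8 = 2. Three days at the lower dose are skipped in each.

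**Reading 2: the level after the one where the replaced participant stopped.** Fold = next level / planned Day 1 dose; days skipped = 3 × number of levels omitted.

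| Panel | Replaced participant stopped at | First dose of replacement | Fold over planned start | Days skipped |
|---|---|---|---|---|
| C | 4 mg | 8 mg | 8/4 = 2 | 3 |
| C | 8 mg | 12 mg | 12/4 = 3 | 6 |
| C | 12 mg | 16 mg | 16/4 = 4 | 9 |
| C | 16 mg | 20 mg | 20/4 = 5 | 12 |
| C | 20 mg | 24 mg | 24/4 = 6 | 15 |
| D | 8 mg | 16 mg | 16/8 = 2 | 3 |
| D | 16 mg | 24 mg | 24/8 = 3 | 6 |
| D | 24 mg | 36 mg | 36/8 = 4.5 | 9 |
| D | 36 mg | 48 mg | 48/8 = 6 | 12 |

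If the Panel D fallback were in force, the top case would be 48/4 = 12-fold its own 4 mg start, so 6-fold does not overstate the range.

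**Who is exposed.** Replacements generally keep the replaced participant's assignment. Active assignments are 9/12 = 75% in Panel C and 12/20 = 60% in Panel D. Replacements on placebo are not exposed.

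**Do other provisions limit a first dose?**

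- Section 8.12 caps the maximum daily dose, which is the top of the ladder and so equals the worst case.
- Section 4.2.1.1 stops further up-titration for persistent moderate EPS, which presupposes that the participant has already been dosed.
- Section 6.6 relies on data from previous dose levels; a new participant has none.
- Down-titration in Section 4.1, rescue medication in Section 6.5.1 and confinement in Section 8.1.12 act after the dose or do not concern its size.

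**Monitoring, conditional on how days are counted.** If Schedule of Activities days ran from the replacement's own first dose, footnotes c and g of the Panels A, B and C table would give a Panel C participant no scheduled postdose heart rate or blood pressure before Day 8 and no postdose ECG before Day 9. If days follow the dose level, this gap shrinks or disappears. Section 5.5 does not say which applies.

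**The case against.** The best case for leaving the text alone has five parts.

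1. **Titration from the first level is the default.** Section 5.5 says a replacement generally gets the same intervention or sequence, and Section 4.1 starts every participant randomized to MK-8189 at 4 mg or 8 mg. The disputed sentence only adds an option, and review comes before the dose. This stands, and it limits the severity. But the option has no bounds, and the review has nothing to apply.

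2. **The narrow reading is more natural.** The sentence refers to the panel's dose level, not to where the replaced participant stopped. That is fair, and on this reading the Panel C start is 8 mg, which Section 4.3.1 partly supports. Panel D still allows a first dose of 16 mg, for which the readable text offers neither a rationale nor a check like the four-participant one used for 8 mg.

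3. **Support for higher starts may lie in text that cannot be seen.** Section 2.2.2 is largely not shown and the occupancy data are redacted. This is a real limit, so the claim is confined to the readable text. Hidden data would still not define the level or supply a criterion in Section 5.5.

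4. **Fold in milligrams is not fold in risk.** Section 4.3.3 says occupancy flattens at higher doses. That is correct, and the 6-fold figure should not be read as 6-fold risk. But that argument is made for a step from 24 mg to 48 mg in people already titrated, not for going from no drug to either dose.

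5. **A narrower repair would do, such as capping the start at the second level.** That would remove the worst case but still leave an unchecked 16 mg first dose in Panel D.

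**Conclusion.** The concern holds and should be fixed. As written, one sentence permits a first dose anywhere from 8 mg to 24 mg in Panel C and from 16 mg to 48 mg in Panel D. That is 2-fold to 6-fold the planned start, with 3 to 15 days (Panel C) or 3 to 12 days (Panel D) of titration omitted. Even the narrow reading departs from the within-participant titration that the rest of the protocol relies on.

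The figures assume the planned ladders with 3 days per level and a replacement on active drug. Which reading was intended is unknown. The documents give no dropout timing, so frequency cannot be estimated. Because the permission is discretionary and follows joint review, this is a defect to correct, not evidence that participants would in fact be started at the top doses.

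**What to change.** Replace the last sentence of Section 5.5 with:

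> A replacement participant will begin at the first dose level in force for that panel on Day 1 and follow that panel's titration schedule and Schedule of Activities.

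The words *in force* keep the option of a 4 mg start in Panel D if the initial cohort leads to it. Tying the replacement to the panel's Schedule of Activities also settles which days apply.

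**Cost.** One sentence of text, plus longer participation per replacement than under a late start, assuming a late starter takes only the remaining levels for 3 days each. On Reading 1 this is 18 − 15 = 3 extra dosing and confinement days in Panel C and 15 − 12 = 3 in Panel D. On Reading 2 the maximum is 18 − 3 = 15 in Panel C and 15 − 3 = 12 in Panel D. In Panel D these are also extra days off antipsychotics. Section 4.1 notes that participants in Panels B and D "have a risk to experience exacerbations in psychotic symptoms both during the washout period as well as during the MK-8189 treatment period". The total never exceeds the 18 or 15 dosing days planned for every original participant.

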6 STUDY INTERVENTION

Study intervention is defined as any investigational intervention(s), marketed product(s), placebo, or medical device(s) intended to be administered to a study participant according to the study protocol.

Clinical supplies, MK-8189 and matching placebo, will be packaged to support enrollment. Clinical supplies will be affixed with a clinical label in accordance with regulatory requirements.

